# 7. Vertical transmission risk and outcomes: comprehensive statistical analysis

As discussed in the previous section, an analysis of VTR and the risk of severe outcomes among the vertically infected comprises several inter-related components: test persistence; test sensitivity and specificity; surveillance data; gestational age at maternal infection; as well as vertical transmission and outcomes of vertical transmission. The relationships between these evidence sources and the model parameters to be estimated can be set out schematically as an influence diagram (Figure 1). Using the influence diagram, we can describe the separate components of the statistical analysis. We will throughout assume a Bayesian framework. This is partly because prior information on test

Author: [name] (UNIVBRIS)

18

persistence, sensitivity, specificity and cross-reactivity plays an essential role in achieving unbiased estimates, and because there is a need to "update" the prior persistence information using the ZIKA-VT data. In addition, GA at maternal infection must be characterized as a *distribution*, which will be informed by a combination of persistence and surveillance data.

#### 7.1 Vertical transmission rate

Assume that for each woman i we will have estimates of the probability  $\pi_i(t)$  that the onset of her infection occurred in week t. We assume that vertical transmission can only occur if infection exists during pregnancy, so that the *onset* is in the interval  $-2 \le t \le G_i$  where  $G_i$  is the gestational age at delivery. If the probability of vertical transmission given maternal infection at week t is V(t), then the probability of in utero transmission in women i is:

$$v_i = \sum_t V(t)\pi_i(t), \quad Y_i \sim Bern(v_i)$$
(7.1)

The outcome data  $Y_i=0,1$  (1 indicating Vertical infection (VI), 0 indicating no VI in a child born to women i), is a Bernoulli realization of the parameter  $v_i$ . In a Bayesian framework, we can attribute a vague prior to V(t) and use the data obtain posterior distributions for V(t),  $v_i$ , and  $\pi_i(t)$  given the Bernoulli likelihood.

In practice, a smooth parametric or semi-parametric function would be fitted to V(t). The analysis is readily extended to include additional risk factors  $\mathbf{X}_i$  with coefficients  $\boldsymbol{\beta}$ :

$$logit(v_i) = logit(\sum_t V(t)\pi_i(t)) + \boldsymbol{\beta}^T \mathbf{X}_i$$

#### 7.2 Risk of severe outcomes of congenital infection

A similar form of analysis will be carried out for severe outcomes of congenital infection. The precise definition remains to be determined, but could include: fetal death, stillbirth, microcephaly, cranial disproportion, or ZIKV-related death within the first two years. The analysis will estimate the risk of severe outcomes conditional on vertical transmission having taken place. This clarifies that there may be two distinct processes: risk factors for congenital infection, and risk factors for severe damage given congenital infection.

The form of analysis for severe clinical outcomes conditional on vertical infection parallels that for vertical transmission rate. Here,  $c_i$  is the risk of severe outcomes in a child born to women i, and C(t) is the probability of severe outcomes given maternal infection in week t. Data  $Z_i=0,1$  indicating severe (1) or non-severe (0) outcomes is a Bernoulli realization of  $c_i$ , and can be used to update C(t) and  $\pi_i(t)$ :

$$c_i = \sum_t C(t)\pi_i(t), \quad Z_i \sim Bern(c_i)$$

Author: [name] (UNIVBRIS)

19

The analysis can be extended to include risk factors as shown above.

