## 4. ZIKA-SYN: joint statistical analysis

The statistical analysis plans set out in this document are all specifically designed to allow for joint analysis alongside other datasets, both those generated by the other EU-funded ZIKA programs, ZIKA-Plan and ZIKAlliance, and those generated by other non-EU funded consortia such as the ZIP (ZIKA in Pregnancy) study. The joint analysis must of course be absolutely restricted to bona fide prospective vertical transmission studies, a definition of which can be found in Section 5.

As a necessary first step in the design of an SAP, we now state the *properties* that a statistical analysis must have to meet the requirement of a joint statistical analysis in this context. The SAP must be able to deliver unbiased estimates of the target parameters, regardless of:

- 1. Differences between studies in the maternal populations studied, for example symptomatic women only, as opposed to all women.
- 2. Differences between collaborating centers in VTR and risk of adverse clinical outcomes, including residual differences after key covariates are taken into account.
- 3. Differences within and between centers in the temporal scheduling of laboratory tests to identify maternal infection in pregnancy.
- 4. Differences between studies or centers, or changes over time, in the tests used to detect maternal infection in pregnancy, including differences in the combinations of tests, or in the type of tests.
- 5. Difference between studies, or between centers within studies, in test sensitivity, specificity and cross-reactivity.
- 6. Differences between centers in the availability of surveillance data.

It can be shown that the SAP outlined in the following pages has these properties.

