#### 5.3 Gestational age (GA) at maternal infection

In a full data analysis, the target parameter here is not a single date, but a *probability distribution* for each woman, representing when the onset of infection was likely to have occurred, relative to the date of conception which may itself be imperfectly known. To simplify presentation in this SAP we represent this as a discrete distribution in units of one week. Information on the distribution of GA at infection will be derived from one or more of the following

- (a) the date of symptoms, if reported
- (b) dates of a first PCR+ test result and subsequent PCR results
- (c) seroconversion, between last IgG- and first subsequent IgG+
- (d) dates of a first IgM+ and subsequent IgM tests
- (e) dates of an initial IgG+ followed by a rising IgG titer subsequent IgG tests
- (f) avidity tests may also be used to help estimate date of infection, especially in samples that are IgM+ and/or IgG+ at recruitment

Note that an initial PCR+ or IgM+ test result is only informative about timing of infection to the extent that the population distributions of PCR persistence and IgM persistence are known. Thus, test persistence information will be critical in estimating GA at maternal infection (see *Section 7.4*).

In practice, if the tests all had perfect sensitivity and specificity, the sequence of test results would either indicate no maternal infection during pregnancy, or it would define an *interval* during which infection has occurred. The persistence distributions, if relevant, will impact on the probability distribution of GA at infection *within* that interval. The issue of test accuracy adds a further layer of complexity, discussed in the next section.

A third source of information is the weekly local surveillance of incident cases of confirmed or suspected ZIKV, DENV and CHIKV [4]. If we reasonably assume that the attack rates in the general population are proportional to attack rates in the pregnant women being recruited, the surveillance data represents an *a priori* distribution of GA at maternal infection within the interval defined by the sequence of tests. The PCR or IgM persistence distributions, if relevant, will combine with the surveillance information to define maternal GA at infection.

Author: [name] (UNIVBRIS)

16

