#### 7.5.1 Estimating the persistence distribution of a single test

The objective here is to estimate the parameters  $\theta$  of the persistence distribution  $F(d,\theta)$  from data  $U_{Li}$ ,  $U_{Ri}$ ,  $W_{Li}$ ,  $W_{Ri}$  for every woman i, taking the following general form:

This represents a sequence of tests -++-, starting with a "last –ve" before the infection occurs at  $U_L$  and a first +ve after the infection at  $U_R$ . The onset of infection is within this interval. The date at which the test turns negative is between the last +ve at  $W_L$  and the first –ve at  $W_R$ . In practice, we may not observe a sequence -++- in a series of IgM or PCR tests in every woman. However, in combination with the occurrence of symptoms and the results of IgG tests, it will be possible to construct definite dates  $U_{Li}$ ,  $U_{Ri}$ ,  $W_{Li}$ ,  $W_{Ri}$  for every woman i who tests +ve on either IgM or PCR. For example, if symptoms occur at time T then  $U_{Li} = U_{Ri} = T$ ; if no final –ve test is observed, then  $W_{Ri} = W_{Li} + D$ ; if no initial –ve test is observed, then  $U_{Li} = U_{Ri} - D$ ; and so on. Note, also, that if a baby born to women i is confirmed to be congenitally infected, then this information requires that  $-2 \le t \le G$ ; in other words,  $U_{Li} \ge -2$  and  $U_{Ri} \le G_i$ .

If the data indicates that the GA of maternal infection is at t,  $U_{Li} \le t \le U_{Ri}$ , then the probability of the data given that t = T is:

$$\Pr(U_{L_i}, U_{R_i}, W_{L_i}, W_{R_i} \mid t = T, \theta) = \begin{cases} F(W_{R_i} - T - 1, \theta) - F(W_{L_i} - T - 1, \theta) & U_{L_i} \le T \le U_{R_i} \\ 0 & \text{otherwise} \end{cases}$$

Therefore, averaging over the distribution of maternal infection  $\pi_i(t)$ , the likelihood for the data is:

$$\Pr(U_{Li}, U_{Ri}, W_{Li}, W_{Ri} \mid \pi_i(t), \theta) = \sum_{i} \pi_i(t) (F(W_{Ri} - t - 1, \theta) - F(W_{Li} - t - 1, \theta)), U_{Li} \le t \le U_{Ri}$$

If the onset of infection at  $t_S$  is observed,  $U_{Li} = t_S = U_{Ri}$  and  $\pi_i(t_S) = 1$ , and the likelihood reduces to the standard likelihood for right censored or right interval censored data.

Author: [name] (UNIVBRIS)

22

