#### 8.1 Analyses to be carried out

Note that the estimates of incidence and seroprevalence that can be generated directly from ZIKA-VT are not true population estimates, because, within each collaborating center, the intention is to recruit pregnant women from areas at higher risk of arbovirus infection, and during periods of higher incidence. However, there is an interest in estimating incidence because it may correlate with risk of transmission or adverse clinical outcomes, if for example, both are related to viral load or degree of susceptibility.

All analyses will be initially stratified by center and mosquito season, or by center and year if there is no mosquito season. The text under each heading below should be understood as specifying one or more tables, in most cases separately for each of the three arboviruses.

8.1.1 Basic demographics of the sampled population. We will tabulate the numbers recruited each season, their age distribution. Further breakdowns will be by: socio-economic class, income range, type of housing, area of residence, residence stratified by arbovirus infection incidence (from surveillance data), as considered appropriate

8.1.2 Seroprevalence and cumulative incidence. For each arbovirus, the denominator for a seroprevalence estimate is the number of women who had at least one IgG test, and the numerator is the number who were IgG+ on their first test. In addition to "crude" (without adjustment) estimates of seroprevalence, we will obtain estimates of cumulative incidence  $\pi$ , which is (observed) seroprevalence p adjusted for IgG sensitivity and specificity, using the relationship

$$p = \pi Se + (1 - \pi)(1 - Sp)$$

Author: [name] (UNIVBRIS)

26

The sensitivity and specificity will be characterized as probability distributions based on the data available, assembled under the ZIKA-VID work package. The sources of this data will be continually updated (see *Appendix 4*).

If more than one test was used, results will be reported separately for each test (see Table 5)

The adjustment can be extended to account for cross-reactivity between DENV and ZIKV IgG tests, given information on sensitivity, general false positive rates, and cross-reactivity of both assays:

$$p_{Z} = \pi_{Z} S e_{Z} + (1 - \pi_{Z})(1 - S p_{Z}) + \pi_{D} X r_{Z}$$

$$p_{D} = \pi_{D} S e_{D} + (1 - \pi_{D})(1 - S p_{D}) + \pi_{Z} X r_{D}$$

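### If fetal death stays in the severe-outcome composite, the Section 7.2 model under-estimates C(t) for infections dated before enrolment, by an amount that varies with recruitment week

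*SAP*

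**What the plan says.** Section 7.2 sets out the analysis of severe outcomes of congenital infection. On the definition it says "The precise definition remains to be determined", and that it "could include: fetal death, stillbirth, microcephaly, cranial disproportion, or ZIKV-related death within the first two years". C(t) "is the probability of severe outcomes given maternal infection in week t", and the data enter as Z_i ~ Bern(c_i) with c_i = Σ C(t)π_i(t). The only conditioning stated is on vertical infection: "The analysis will estimate the risk of severe outcomes conditional on vertical transmission having taken place".

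Three other places decide who contributes to C(t), and at which week.

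- **Entry.** Section 8.1 says "the intention is to recruit pregnant women from areas at higher risk of arbovirus infection, and during periods of higher incidence". Women therefore enter during pregnancy. The SAP does not give the gestational age at entry.
- **Back-dating.** Section 5.3 brings in infections that precede entry, with avidity testing to help date them, "especially in samples that are IgM+ and/or IgG+ at recruitment". Section 7.5.1 moves the earliest possible onset back by the maximum marker duration D "if no initial –ve test is observed". Where the child is congenitally infected, Sections 7.4.6 and 7.5.1 confine onset to week −2 or later.
- **Prospective rule.** Section 5 requires maternal infection to be ascertained independently of fetal outcome, so a woman cannot be added because she lost a pregnancy.

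On time-to-event methods, Section 10.2 provides for right censoring of categorical pediatric outcomes. Neither Section 7 nor Section 10.2 mentions left truncation or delayed entry.

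**The concern.** A woman dated to infection at week 6 and recruited at week 12 counts as a full observation of risk from week 6. A woman infected at week 6 whose pregnancy ended at week 9 cannot be in the data. The first is present only because the outcome had not yet happened, and the likelihood ignores this.

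Section 10.4 names severe outcome given vertical transmission as one of the study's two fundamental outcomes, and Section 2.1 makes gestational age at infection the main determinant to be studied. The distortion falls on the early weeks of that curve. It also depends on when a centre enrols. Two centres with the same true risk but different recruitment weeks would produce different C(t), and the centre differences allowed for in Sections 2.1 and 4 could absorb this as real variation. That matters for a plan written to support pooling with other consortia.

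**Working it through.** The SAP states no value for C(t), fetal-loss risk or recruitment week, and Section 10.3 reports no formal sample-size calculation. There is no figure to reproduce. The check is algebraic, followed by an illustration on assumed inputs.

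**What the model estimates.** Take vertically infected pregnancies with infection at week t, and let q be the probability of fetal death between t and recruitment at week R. A fraction 1 − q is recruited. All deaths before R would have been severe outcomes, so the severe outcomes still to be seen make up C − q. The Bernoulli model fitted to recruited women therefore targets

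(C − q)/(1 − q),

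and the shortfall is C − (C − q)/(1 − q) = q(1 − C)/(1 − q). This is positive whenever q > 0 and C < 1. If infection follows recruitment, q = 0 and there is no bias.

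**Assumed inputs** (none from the SAP): infection week known to be 6; total fetal-loss risk L = 10% at a constant weekly hazard over K = 8 or 20 weeks; another severe outcome in m = 10% of survivors. Then

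- C = L + (1 − L)m = 0.10 + 0.90 × 0.10 = 19.0%
- h = −ln(1 − L)/K = 0.1054/8 = 0.0132 per week, or 0.1054/20 = 0.0053 per week
- q = 1 − exp(−h × weeks from infection to recruitment, up to K)

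For recruitment at week 12, six weeks after infection:

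- K = 8: q = 7.6%, and (0.190 − 0.076)/(1 − 0.076) = 12.3%
- K = 20: q = 3.1%, and (0.190 − 0.031)/(1 − 0.031) = 16.4%

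Estimated C by recruitment week (truth 19.0%):

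| Recruitment week | K = 8 | K = 20 |
|---|---|---|
| 6 | 19.0% | 19.0% |
| 8 | 16.8% | 18.1% |
| 12 | 12.3% | 16.4% |
| 16 | 10.0% | 14.6% |
| 20 | 10.0% | 12.8% |

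Other assumed cases at recruitment week 12 with K = 8: 9.8% falls to 6.2% (L = 5%, m = 5%), and 28.0% falls to 14.9% (L = 20%, m = 10%). For infection at week 22, after every recruitment week tried, the estimate stays at 19.0%.

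**What delayed entry recovers.** A simulation of 400,000 pregnancies (L = 10%, m = 10%, K = 8, infection at week 6) compared the Section 7.2 model with a left-truncated estimate:

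| Recruitment spread over weeks | Section 7.2 model | Delayed entry |
|---|---|---|
| 6–8 | 18.0% | 19.1% |
| 8–12 | 14.7% | 16.8% |
| 10–16 | 11.6% | 14.6% |
| 16–20 | 10.0% | 10.0% |

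Delayed entry recovers the full risk only when some women are observed from infection onwards. Otherwise it gives the risk conditional on survival to the earliest recruitment week. With the earliest entry at week 8, for example, it gives the 16.8% found in closed form for R = 8.

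**The case against.** The strongest reply is that the fault is conditional. The composite is not settled, and fetal death is only a candidate component. If it is reported separately, the mechanism for C(t) largely disappears. That stands, and the point is limited accordingly. Table 3 already tabulates fetal deaths by trimester, and Section 7.7 carries the gestational-age probabilities into such analyses, so some separation is planned. Those tables draw on the same recruited women, however, and do not deal with late entry.

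A reader might go further in four ways that the documents do not support.

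- **That the result contradicts Section 4.** Section 4 says "The SAP must be able to deliver unbiased estimates of the target parameters, regardless of" six listed differences. Gestational age at recruitment is not one of them, so the supportable point is an omission from the list.
- **That fetal death is fully ascertained after enrolment.** Section 5.2 classes a fetus as infected on a PCR-positive fetal, placental or amniotic specimen. A loss without a specimen may not count as vertically infected.
- **That V(t) is biased in the same way.** That would need infected fetuses to be lost before enrolment more often than uninfected ones, and the SAP gives nothing from which to judge this.
- **That delayed entry removes the dependence on recruitment week.** The simulation shows that it does so only in part, and not at all when everyone enters after the period of risk. Any cohort that enrols during pregnancy shares this limit.

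**Conclusion.** The point holds in conditional form. If fetal death is in Z, Section 7.2 estimates (C − q)/(1 − q) for infections dated before enrolment. The direction is certain whenever some infected pregnancies are lost before recruitment and C is below 1, and the estimate varies with recruitment week. Infections after enrolment carry no such bias.

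The size cannot be derived from the SAP. The fall from 19.0% to between 12.3% and 16.4% at recruitment week 12 rests on an assumed infection week, loss risk, loss duration and risk in survivors. It shows that the effect can be material, and is not a prediction for this study. Because the definition is still open, this can be settled before analysis.

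**What to change.** In Section 7.2:

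- Separate fetal loss from severe outcomes in survivors.
- Model fetal loss as a weekly hazard on the gestational-age scale, with each woman entering the risk set at her week of enrolment.
- State that, for infection weeks before enrolment, C(t) is the risk conditional on survival to the earliest gestation under observation.

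Use week of entry in the centre and cross-study comparisons, and add gestational age at recruitment to the list in Section 4.

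The cost is SAP wording and model code, plus a recorded week of entry for each woman. The SAP does not say that this is recorded, and Section 5.3 notes that the date of conception may be uncertain. Early-week estimates will be less precise, and losses before any infected woman was under observation remain unidentifiable.

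### SAP 7.2 leaves out the V(t) weight that its conditional target needs, and SAP 7.1 applies covariates after averaging over infection week; both can bias results where timing or infection is uncertain

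*SAP*

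**What the plan says.** Section 7.1 models vertical infection as Y_i ~ Bern(v_i) with v_i = Σ V(t)π_i(t), where π_i(t) is the probability that the mother's infection began in week t. It continues: "The analysis is readily extended to include additional risk factors", and does so by adding β'X_i to the logit of the sum already taken over weeks.

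Section 7.2 turns to severe outcomes: "The analysis will estimate the risk of severe outcomes conditional on vertical transmission having taken place". The next paragraph repeats that the analysis is conditional on vertical infection, but then says that "C(t) is the probability of severe outcomes given maternal infection in week t". The model is Z_i ~ Bern(c_i) with c_i = Σ C(t)π_i(t), using the same π_i(t) as 7.1. The severe-outcome data "can be used to update C(t) and" π_i(t). On covariates, 7.2 adds: "The analysis can be extended to include risk factors as shown above".

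Four other places bear on this:
- 7.4.6 and 7.5.1 restrict the onset date to pregnancy when the infant is congenitally infected.
- 7.4 and 7.7 allow π_i(t) to sum to less than 1 over pregnancy.
- Section 4 requires unbiased estimates regardless of which tests are used and when, and asserts that the plan has this property.
- 10.4 names severe outcome given transmission as one of two fundamental outcomes.

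**The concern.** The stated target and the printed equation in 7.2 do not match. Learning that an infant was vertically infected changes the likely infection week whenever transmission risk depends on that week. The timing distribution for infected infants is therefore tilted by V(t), and averaging C(t) over the untilted distribution answers a different question. Estimating the role of gestational age is the stated objective in 2.1, so V(t) and C(t) cannot be assumed flat.

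The covariate term in 7.1 raises a related problem of order. An odds ratio for transmission should act on V(t). Placed on the averaged v_i, it acts on a probability that also contains the chance that the mother was not infected in pregnancy. Its value then depends on how certain the diagnosis is, and hence on the tests and their schedule, which is the dependence Section 4 rules out.

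**Working it through.** The SAP gives no values for V(t) or C(t), and 10.3 says there is no consensus on the rates, so there is no plan figure to reproduce. All V, C and odds ratios below are assumptions.

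**Severe outcome: algebra.**
Correct: P(severe | vertically infected) = Σ π V C / Σ π V.
SAP: Σ π C.
Correct minus SAP = Cov_π(V, C) / E_π(V). This is zero if π_i is a point mass (a dated infection, 7.4.1), or if V or C is flat over the interval.

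**Severe outcome: illustration.** Take V = 0.1/0.3/0.6 and C = 0.50/0.20/0.05 by trimester, with π = 1/3 each (timing wholly unknown).
- Correct: (0.05 + 0.06 + 0.03)/(0.1 + 0.3 + 0.6) = 0.14.
- SAP: (0.50 + 0.20 + 0.05)/3 = 0.25.
- Check: Cov = 0.14/3 − (1/3)(0.25) = −0.0367; divided by 1/3 this is −0.11, and 0.25 − 0.11 = 0.14.
- Shallower V = 0.2/0.3/0.4: (0.10 + 0.06 + 0.02)/0.9 = 0.20 against 0.25.
- Flat V: 0.25 against 0.25.

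**Dependence on the timing window.** Weeks −2 to 40, logit-linear V and C, uniform π.

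| V over pregnancy | C | Window | Correct | SAP | Ratio |
|---|---|---|---|---|---|
| .05 to .70 | .60 to .05 | whole pregnancy | .155 | .260 | 1.68 |
| .10 to .40 | .60 to .05 | whole pregnancy | .197 | .260 | 1.32 |
| flat | .60 to .05 | whole pregnancy | .260 | .260 | 1.00 |
| .40 to .10 | .60 to .05 | whole pregnancy | .326 | .260 | 0.80 |
| .40 to .10 | .30 to .05 | 26 weeks | .155 | .144 | 0.93 |
| .40 to .10 | .30 to .05 | 12 weeks | .159 | .157 | 0.98 |

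For windows up to 12 weeks the error was about 5% or less in every case tried. Its direction reverses when V falls with gestation.

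**Does the stated updating of π_i(t) supply the weight?** As written, Y_i and Z_i are separate Bernoulli draws that share π_i but no infection week. With π_i fixed they are independent, so observing Y_i = 1 changes nothing for Z_i. With the Dirichlet of 7.4.3 and total count A, the implied risk is
P(Z=1 | Y=1) = (A × SAP average + correct value)/(A + 1).
In the trimester illustration:
- A = 10: (2.5 + 0.14)/11 = 0.24.
- A = 100: (25 + 0.14)/101 = 0.249.

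Only 1/(A + 1) of the error is removed: 9% at 10 surveillance counts and 1% at 100.

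**Covariates where π_i sums to less than 1.** Let P = Σπ_i over pregnancy. Take V = 0.30 and a true odds ratio of 3: odds 0.30/0.70 × 3 = 1.286, so V becomes 0.5625.
- P = 10/15: v = 0.20 and 0.375. Odds ratio (0.375/0.625)/(0.20/0.80) = 2.40.
- P = 1/5: v = 0.06 and 0.1125. Odds ratio (0.1125/0.8875)/(0.06/0.94) = 1.99.

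Both values of P come from the false-positive illustration in 7.6.

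**Coherence.** Take P = 0.2, V = 0.6 and odds ratio 3. The SAP form gives odds 0.12/0.88 × 3 = 0.409, so v_i = 0.29. That exceeds the 0.2 probability of any infection in pregnancy, although 7.1 assumes transmission needs such an infection. Inside the sum: odds 1.5 × 3 = 4.5, V = 0.818, and v_i = 0.2 × 0.818 = 0.164.

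**Covariates where π_i sums to 1.** With a true odds ratio of 2 and V rising .05 to .70, the SAP form gives 2.00 for a dated infection, 1.97 for a 12-week window, 1.88 for 26 weeks and 1.73 for the whole pregnancy. With V from .10 to .40 and the whole pregnancy it gives 1.93; with flat V, 2.00. The largest effect seen was 5 falling to 3.51 (steep V, whole pregnancy).

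**The case against.** The best defence is that 7.1 and 7.2 say the outcome data update π_i(t), and 7.7 joins everything in one integrated analysis. If π_i(t) in 7.2 meant the timing distribution after vertical infection has been observed, Bayes' rule would make it V(t)π_i(t)/ΣV(u)π_i(u), and c_i = Σ C(t)π_i(t) would be correct. The SAP does not say this. It uses one symbol for both models, and its separate Bernoulli draws do not produce that result. Figure 1 is not available here, so it can neither support nor undermine this defence.

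Other parts of the defence stand:
- The conditional target is stated twice, so the definition of C(t) may be loose wording. The missing weight remains even if it is.
- A reader might infer that 7.2 makes no allowance for vertical infection at all. That is too strong: 7.4.6 and 7.5.1 confine onset to pregnancy. They do not reweight weeks within it.
- Because of that restriction, dilution from π_i summing to less than 1 concerns 7.1 and does not carry into 7.2. When π_i sums to 1, what remains is largely non-collapsibility of the odds ratio.
- The probabilities 0.67 and 0.2 come from an illustration of a lone IgM test with 95% specificity. The SAP plans confirmatory tests and hopes for high specificity of the whole algorithm, so these are not expected operating values.
- The SAP describes important elements of itself as generic and simplifies some notation, though it does not say so of 7.2.

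**Conclusion.** The equations are wrong as written. The 7.2 formula does not deliver its stated conditional risk, because C(t) is not defined given vertical infection and the V(t) weight is absent. The 7.1 covariate term acts on the wrong scale when infection in pregnancy is uncertain and can then give an impossible probability. Both conflict with the Section 4 claim, since the error varies with how precisely tests date and confirm infection.

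It would be tempting to conclude that the two fundamental outcomes are biased outright. The document does not support that. With π_i summing to 1 there is no bias for dated infections or flat V, nor, for the severe outcome, for flat C. In the cases tried, the severe-outcome error is about 5% or less for windows up to 12 weeks. It becomes material with wide timing windows when V and C both vary, and its direction depends on their unknown shapes. The contrast of 0.14 with 0.25 is the extreme of wholly unknown timing under assumed values. The covariate attenuation is mostly modest when π_i sums to 1 and substantial mainly when it does not. The SAP calls these outcomes fundamental, not primary.

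**What to change.** Rewrite 7.1 and 7.2 around a shared latent infection week t for each mother:
- Define C(t) as the risk of a severe outcome given vertical infection with maternal onset in week t.
- Y_i | t ~ Bern(V_i(t)) and Z_i | Y_i = 1, t ~ Bern(C_i(t)).
- Covariates inside the sum: logit V_i(t) = logit V(t) + β'X_i and logit C_i(t) = logit C(t) + γ'X_i.
- Then v_i = Σ π_i(t)V_i(t) and, for infected infants, c_i = Σ π_i(t)V_i(t)C_i(t) / Σ π_i(t)V_i(t).

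State in 7.2 that π_i(t) is the mother's timing distribution before the infant's outcome is used, so that the V(t) weight is not applied twice. The cost is a revision of the SAP formulas and the model code. The data to be collected do not change, and the Bayesian software options in 7.8 remain open.
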